3.1.1 Trial Stopping Rules

All safety information will be carefully analysed by the sponsor. Enrollment will be temporarily stopped if one of the following conditions is met;

- >20% of patients treated in the trial develop Grade 3 osteoporosis or another bone-related DLT
- ≥ 2 patients treated in the trial develop a serious pathologic fracture
- >20% of patients at a certain dose level experience a Grade 3 cytokine release syndrome (CRS) and/or Grade 3 hypersensitivity reaction and/or Grade 3 infusion reaction
- One patient experiences a Grade 4 CRS and/or Grade 4 hypersensitivity reaction and/or Grade 4 infusion reaction

If this occurs, the SMC will conduct an in-depth analysis of the safety profile of BI 905681 and the benefit-risk profile of BI 905681 will be re-assessed. This assessment will be used to determine if the study should be continued as planned, permanently discontinued or whether the study should continue with modification to the protocol to adequately mitigate patient risk and to ensure that the benefit-risk assessment for continued investigation of BI 905681 remains positive. The SMC will also consider and provide guidance for the management of patients who are currently on treatment. The outcome of the analysis and the recommendations will be shared with all involved regulatory health authorities prior to a planned re-start of enrollment. In case the benefit-risk assessment is no longer considered to be positive, the trial will be discontinued.

3.2 DISCUSSION OF TRIAL DESIGN, INCLUDING THE CHOICE OF CONTROL GROUP(S)

Dose escalation and cohort size will be determined based on the recommendation of the SMC, guided by a BLRM with overdose control. An EWOC design will increase the chance of treating patients at efficacious doses while reducing the risk of overdosing. This design is based on practical experience and is an efficient method due to its ability to identify the dose

with a desired toxicity rate and its allocation of a greater proportion of patients to doses at, or close to, that desired dose ([R13-4802](#), [R13-4804](#), [R13-4805](#)). The use of Bayesian models for Phase I studies has also been advocated by the European Medicines Agency (EMA) guideline on small populations ([R07-4856](#)) and by the US Food and Drug Administration (FDA) ([R13-4881](#)).

3.3 SELECTION OF TRIAL POPULATION

Patients with advanced, unresectable and/or metastatic solid tumours who are either refractory after standard therapy for the disease or for whom standard therapy is not appropriate will be eligible. The trial will be conducted in approximately 5 sites and it is anticipated that approximately 60 patients (30 per dosing schedule) will be enrolled in the trial. The total number of patients will depend on the number of dose escalations necessary.

A log of all patients enrolled into the trial (i.e. who have signed informed consent) will be maintained in the Investigator Site File (ISF) at the investigational site irrespective of whether they have been treated with investigational drug or not.

Assessments may be repeated within the Screening period if patients do not initially meet the inclusion/exclusion criteria. Eligibility must always be assessed using the latest results available. In addition re-Screening of patients who have previously failed Screening will be permitted. In this situation patients will be handled as a new patient, i.e. sign a new informed consent, allocated a new patient number, and undergo full Screening assessments.

3.3.1 Main diagnosis for trial entry

Patients with histologically or cytologically confirmed advanced, unresectable and/or metastatic solid tumours who are either refractory after standard therapy for the disease or for whom standard therapy is not appropriate.

Please refer to [Section 8.3.1](#) (Source Documents) for the documentation requirements pertaining to the in- and exclusion criteria.

3.3.2 Inclusion criteria

1. Histologically or cytologically confirmed diagnosis of an advanced, unresectable and/or metastatic non-haematologic malignancy. Patient must have measurable or evaluable lesions (according to RECIST v 1.1).
2. Patient who has failed conventional treatment or for whom no therapy of proven efficacy exists or who is not eligible for established treatment options.
3. Patients (only those who harbour a historically confirmed RNF43 mutation or R-spondin fusion) willing to undergo mandatory tumour biopsy at the time points specified in the protocol.
4. Eastern Cooperative Oncology Group (ECOG) Score of 0 or 1 ([R01-0787](#)).
5. Adequate organ function defined as all of the following:

Proprietary confidential information © 2019 Boehringer Ingelheim International GmbH or one or more of its affiliated companies

- Absolute neutrophil count (ANC) $\geq 1.5 \times 10^9/L$; haemoglobin $\geq 9.0 \text{ g/dL}$; platelets $\geq 100 \times 10^9/L$ without the use of haematopoietic growth factors within 4 weeks of start of study medication.
- Total bilirubin $\leq 1.5 \times$ the upper limit of normal (ULN), except for patients with Gilbert's syndrome: total bilirubin $\leq 3 \times$ ULN or direct bilirubin $\leq 1.5 \times$ ULN.
- Creatinine $\leq 1.5 \times$ ULN. If creatinine is $>1.5 \times$ ULN, patient is eligible if concurrent creatinine clearance $\geq 50 \text{ ml/min}$ (measured or calculated by the Chronic Kidney Disease Epidemiology Collaboration (CKD-EPI) formula or Japanese version of CKD-EPI formula for Japanese patients).
- Aspartate transaminase (AST) and alanine transaminase (ALT) $\leq 3 \times$ ULN if no demonstrable liver metastases, or otherwise $\leq 5 \times$ ULN
- Alkaline Phosphatase (ALP) $< 5 \times$ ULN

6. Recovered from any previous therapy-related toxicity to \leq CTCAE Grade 1 at start of treatment (except for alopecia and stable sensory neuropathy which must be \leq CTCAE Grade 2).
7. At least 18 years of age at the time of consent or over the legal age of consent in countries where that is greater than 18 years.
8. Signed and dated written informed consent in accordance with ICH-GCP and local legislation prior to admission to the trial
9. Life expectancy ≥ 3 months at the start of treatment in the opinion of the investigator
10. Male or female patients. Women of childbearing potential (WOCBP)² must only be included after a confirmed menstrual period within the past 4 weeks and a negative pregnancy test at Screening. WOCBP with irregular menstruation may be included after two negative pregnancy tests during Screening between 2 and 4 weeks apart. WOCBP and men able to father a child must be ready and able to use highly effective methods of birth control per ICH M3 (R2) that result in a failure rate of less than 1% per year when used consistently and correctly. These methods must be used during the study and for at least 4 months after the last dose of BI 905681. A list of contraception methods meeting these criteria is provided in the patient information.

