	
of the investigator
 
Male or female patients. Women of childbearing potential (WOCBP)¹ must only be included after a confirmed menstrual period within the past 4 weeks and a negative pregnancy test at Screening. WOCBP with irregular menstruation may be included after two negative pregnancy tests during Screening between 2 and 4 weeks apart. WOCBP and men able to father a child must be ready and able to use highly effective methods of birth control per ICH M3 (R2) that result in a failure rate of less than 1% per year when used consistently and correctly. These methods must be used during the study and for at least 4 months after the last dose of BI 905681. A list of contraception methods meeting these criteria is provided in the patient information. 
Exclusion criteria
 
Major surgery (major according to the investigator's assessment) performed within 4 weeks prior to first trial treatment or planned within 6 months after ScreeningPrevious or concomitant malignancies other than the one treated in this trial within the last 2 years, except:
effectively treated non-melanoma skin cancerseffectively treated carcinoma in situ of the cervixeffectively treated ductal carcinoma in situother effectively treated malignancy that is considered cured by local treatmentOsteoporosis \geq CTCAE Grade 2Chronic corticosteroid use, except as permitted for the maintenance therapy of brain metastases (see Exclusion Criterion 13)Osteoporotic compression fracture within 12 months prior to informed consent which is clinically significant in the opinion of the investigator.Patient who must or wishes to continue the intake of restricted medications or any drug considered likely to interfere with the safe conduct of the trial.Previous treatment in this trial.Treatment with a systemic anti-cancer therapy or investigational drug within 28 days or 5 half-lives (whichever is shorter) of the first treatment with the study medication.Any history of or concomitant condition that, in the opinion of the investigator, would compromise the patient's ability to comply with the study or interfere with the evaluation of the safety and
--	---

¹ A woman is considered of childbearing potential (WOCBP), i.e. fertile, following menarche and until becoming post-menopausal unless permanently sterile.

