Permanent sterilisation methods include hysterectomy, bilateral salpingectomy and bilateral oophorectomy.

Tubal ligation is NOT a method of permanent sterilisation.

A postmenopausal state is defined as no menses for 12 months without an alternative medical cause.

	
efficacy of the test drug.
 
• Women who are pregnant, nursing, or who plan to become pregnant or nurse during the trial or within 6 months after the last dose of study treatment.• Active alcohol or drug abuse in the opinion of the investigator.• Patient unwilling or unable to comply with the protocol.• Presence or history of uncontrolled or symptomatic brain or subdural metastases, unless considered stable by the investigator and local therapy was completed. Use of corticosteroids is allowed if the dose was stable for at least 4 weeks. Inclusion of patients with newly identified brain metastasis/es at Screening will be allowed if patients are asymptomatic.• Known history of human immunodeficiency virus (HIV) infection or an active hepatitis B or C infection which in the opinion of the investigator may interfere with participation in the trial.• History of Grade 3 hypersensitivity reactions (including cytokine release syndrome) to monoclonal antibodies.• History of allergy to kanamycin or similar class drugs (including streptomycin, gentamicin, amikacin, tobramycin and neomycin).
Test product(s):	BI 905681
Dose :	Increasing doses of BI 905681 starting at 1.0 mg/kg/q3w. Dose escalation will be guided by a Bayesian logistic regression model (BLRM) with overdose control until the MTD/OBD is reached.
Mode of administration:	Intravenous infusion
Duration of treatment:	Administration will continue until progression of disease (PD), unacceptable toxicity

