3.3.3 Exclusion criteria

1. Major surgery (major according to the investigator's assessment) performed within 4 weeks prior to first trial treatment or planned within 6 months after Screening
2. Previous or concomitant malignancies other than the one treated in this trial within the last 2 years, except:
 - a) effectively treated non-melanoma skin cancers
 - b) effectively treated carcinoma in situ of the cervix
 - c) effectively treated ductal carcinoma in situ

² A woman is considered of childbearing potential (WOCBP), i.e. fertile, following menarche and until becoming post-menopausal unless permanently sterile.

Permanent sterilisation methods include hysterectomy, bilateral salpingectomy and bilateral oophorectomy.

Tubal ligation is NOT a method of permanent sterilisation.

A postmenopausal state is defined as no menses for 12 months without an alternative medical cause.

Proprietary confidential information © 2019 Boehringer Ingelheim International GmbH or one or more of its affiliated companies

- d) other effectively treated malignancy that is considered cured by local treatment
- 3. Osteoporosis \geq CTCAE Grade 2
- 4. Chronic corticosteroid use, except as permitted for the maintenance therapy of brain metastases (see Exclusion Criterion 13)
- 5. Osteoporotic compression fracture within 12 months prior to informed consent which is clinically significant in the opinion of the investigator.
- 6. Patient who must or wishes to continue the intake of restricted medications or any drug considered likely to interfere with the safe conduct of the trial.
- 7. Previous treatment in this trial.
- 8. Treatment with a systemic anti-cancer therapy or investigational drug within 28 days or 5 half-lives (whichever is shorter) of the first treatment with the study medication.
- 9. Any history of or concomitant condition that, in the opinion of the investigator, would compromise the patient's ability to comply with the study or interfere with the evaluation of the safety and efficacy of the test drug.
- 10. Women who are pregnant, nursing, or who plan to become pregnant or nurse during the trial or within 6 months after the last dose of study treatment.
- 11. Active alcohol or drug abuse in the opinion of the investigator.
- 12. Patient unwilling or unable to comply with the protocol.

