4.1.6.1 Re-treatment criteria

Before administering a treatment dose the investigator must review the assessments performed according to the respective Flow Charts ([Schedule A, Table 10.2:1](#) and [Schedule B, Table 10.2:2](#)) and assess eligibility to receive further treatment and check that the following criteria are met:

- Absence of disease progression
- Drug-related AEs recovered to Grade ≤ 1 (or baseline if higher than Grade 1)
- For AEs that do not require a treatment interruption, a toxicity of CTCAE Grade 2 (e.g. hypophosphatemia, anorexia, neuropathy) may be acceptable, provided the investigator considers it safe for the patient to continue treatment

If the criteria for re-treatment are not met, the patient should be evaluated and the next dose of treatment may be delayed until the criteria are met. For patients on Schedule A the dose may be delayed for up to 14 days. For patients on Schedule B, the dose may be delayed for up to 7 days. Dose reduction may be appropriate and will be discussed in the SMC (see [Section 4.1.6.7](#)).

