4.2.2.3 Restrictions regarding women of childbearing potential

Due to the advanced stage of disease of Phase I trial patient populations and the high medical need, females of childbearing potential can be included in this trial provided that they agree to use a highly-effective contraception method. These are methods of birth control per the International Council for Harmonisation (ICH) M3 (R2) that result in a failure rate of less than 1% per year when used consistently and correctly.

Highly-effective methods of contraception include:

- Oral, injected, or implanted hormonal methods of contraception, or
- Intrauterine device or intrauterine system, or
- ‘Double-barrier’ methods of contraception: Male condom in combination with female diaphragm/cervical cap plus spermicidal foam/gel/film/cream.

Details of these contraception methods are described in the patient information in the ICF.

Women of childbearing potential must follow these methods during the trial and for at least 6 months after the end of the trial treatment. Although use of a contraceptive pill is considered a highly-effective method of birth control, women of childbearing potential taking a contraceptive pill must use an additional barrier method for the entire duration of the trial treatment intake and for 6 months after the end of the trial treatment intake.

Male patients with partners of childbearing potential must agree to use condoms and ensure their partner is using an additional highly-effective method of birth control, during the trial and until at least 6 months after the end of the trial treatment.

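### Inclusion criterion 10 and the synopsis ask for at least 4 months of contraception after the last dose, but Section 4.2.2.3 asks for at least 6 (minor inconsistency)

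*Protocol*

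**What the plan says.** Inclusion criterion 10 (Protocol Section 3.3.2) covers women of childbearing potential and men able to father a child. It requires highly effective birth control and fixes the duration: "These methods must be used during the study and for at least 4 months after the last dose of BI 905681". The inclusion criteria in the synopsis give the same period, "for at least 4 months after the last dose of BI 905681".

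Section 4.2.2.3 admits women of childbearing potential "provided that they agree to use a highly-effective contraception method" and then sets a longer period: "Women of childbearing potential must follow these methods during the trial and for at least 6 months after the end of the trial treatment". It gives 6 months again for the extra barrier method required of women taking a contraceptive pill. Male patients with partners of childbearing potential must use contraception "during the trial and until at least 6 months after the end of the trial treatment".

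Exclusion criterion 10, in the synopsis and in Section 3.3.3, bars women who plan pregnancy or nursing during the trial or "within 6 months after the last dose of study treatment". Exclusion criterion 12 bars a "Patient unwilling or unable to comply with the protocol".

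**The concern.** Two operative parts of one protocol give different minimum durations for the same obligation. The shorter one sits in the eligibility list, and Section 8.3.1 requires source evidence that each participant meets every inclusion criterion. A site working from that list would document a commitment to 4 months. The 6-month duty for men is easy to overlook, because it appears only in a subsection whose heading refers to women.

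At stake is the consistency of a reproductive-safety instruction in a first-in-human trial. A patient could be counselled to the shorter period and follow that advice in good faith, yet not comply with Section 4.2.2.3. No estimate or decision rule in the trial depends on this.

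**Working it through.** The plan has no figure to reproduce, so the check sets the texts side by side and tests whether one reading reconciles them.

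| Place | Who | Minimum period | Counted from |
|---|---|---|---|
| Synopsis, inclusion criteria | Women of childbearing potential; men able to father a child | 4 months | Last dose |
| Section 3.3.2, criterion 10 | Same | 4 months | Last dose |
| Section 4.2.2.3 | Women of childbearing potential | 6 months | End of trial treatment |
| Section 4.2.2.3, pill users' extra barrier | Women taking a contraceptive pill | 6 months | End of trial treatment intake |
| Section 4.2.2.3 | Men with partners of childbearing potential | 6 months | End of trial treatment |
| Synopsis and Section 3.3.3, exclusion criterion 10 | Women planning pregnancy or nursing | 6 months (related window, not a contraception rule) | Last dose |

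**Size of the gap.** 6 − 4 = 2 months.

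**Different patients?** No. For women the two groups are identical. For men they overlap: a man able to father a child whose partner is of childbearing potential falls under both rules.

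**Different starting points?** No. Suppose the end of trial treatment is e months after the last dose, with e at least 0. Section 4.2.2.3 then runs to month 6 + e after the last dose, and the gap is (6 + e) − 4 = 2 + e. The difference in wording can only leave the gap at 2 months or widen it.

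**Superseded text?** No. Global Amendment 1 (Section 11.1) changes the flow charts, Section 3.1, Table 4.1.1, Sections 4.1.3 and 4.1.4, and Section 7.1. It does not touch contraception.

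**Test cases, taking e = 0.**
- Stops at month 4: criterion 10 is met (4 ≥ 4) and Section 4.2.2.3 is not (4 < 6).
- Stops at month 6: both are met (6 ≥ 4 and 6 ≥ 6).
- A woman planning pregnancy in month 5 satisfies the duration in inclusion criterion 10 (5 > 4) but is barred by exclusion criterion 10 (5 < 6).

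Six months satisfies every passage; 4 months does not.

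**The case against.** The strongest reply is that there is no true contradiction. Both figures are minima, so 6 months meets both. Criterion 10 can be read as an entry condition and Section 4.2.2.3 as a stricter rule of conduct, and exclusion criterion 12 already removes patients who would not follow it. On that reading 6 months already binds both sexes. This is right about what the protocol as a whole requires, and it keeps the point minor. It does not remove the conflict for a site counselling from criterion 10, and it leaves the 4-month figure with no useful function.

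It is also fair that exclusion criterion 10 is only indirect support, since it concerns plans for pregnancy or nursing and not the duration of contraception. The conflict proper is between criterion 10 with the synopsis and Section 4.2.2.3.

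A reader might infer more than the documents support:

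- *That 4 months is the error, or is too short pharmacologically.* Neither period is derived anywhere. The texts show that the figures differ, not which was intended.
- *That patients were told 4 months.* What the patient information says about duration cannot be seen here.
- *That wrong advice could not be caught later because all contact ends at the follow-up visit.* Section 6.2.3.2 does call that visit the patient's completion of the study. However, both flow charts continue tumour assessments until documented progression and ask that the schedule be kept after early discontinuation where possible. Section 5.2.6.2 also requires adverse events that persist beyond the patient's end of trial to be followed up. The same section requires drug exposure during pregnancy, in a participant or a male participant's partner, to be reported within 24 hours (for a partner, with her written consent), and states no end date.

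**Conclusion.** The inconsistency is real, stands in current text and is minor. The stated minima differ by 2 months for the same patients, and a patient can meet the eligibility criterion while breaching Section 4.2.2.3. This rests on the wording alone and needs no assumption beyond treatment not ending before the last dose. The number of patients affected cannot be derived, and no harm is shown. There is no effect on the BLRM, the MTD or any analysis. SAP Section 4 reports early termination with only Schedule A investigated, so the benefit within this trial is probably small.

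**What to change.** Replace 4 months with 6 months in the synopsis inclusion criteria and in criterion 10 of Section 3.3.2. If the sponsor can document a rationale for 4 months, align Section 4.2.2.3 and both statements of exclusion criterion 10 to it instead. In either case, check that the patient information states the same period.

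The preferred change costs one number in two places plus that check. The downside is up to two more months of contraception for patients who would otherwise have been counselled to 4 months, which Section 4.2.2.3 already requires of them. If no further amendment is written, sites can restate 6 months at the remaining patients' existing end-of-treatment and follow-up visits, and the text should be corrected in any later protocol that reuses it.

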3.3.3 Exclusion criteria

1. Major surgery (major according to the investigator's assessment) performed within 4 weeks prior to first trial treatment or planned within 6 months after Screening
2. Previous or concomitant malignancies other than the one treated in this trial within the last 2 years, except:
 - a) effectively treated non-melanoma skin cancers
 - b) effectively treated carcinoma in situ of the cervix
 - c) effectively treated ductal carcinoma in situ

² A woman is considered of childbearing potential (WOCBP), i.e. fertile, following menarche and until becoming post-menopausal unless permanently sterile.

Permanent sterilisation methods include hysterectomy, bilateral salpingectomy and bilateral oophorectomy.

Tubal ligation is NOT a method of permanent sterilisation.

A postmenopausal state is defined as no menses for 12 months without an alternative medical cause.

Proprietary confidential information © 2019 Boehringer Ingelheim International GmbH or one or more of its affiliated companies

- d) other effectively treated malignancy that is considered cured by local treatment
- 3. Osteoporosis \geq CTCAE Grade 2
- 4. Chronic corticosteroid use, except as permitted for the maintenance therapy of brain metastases (see Exclusion Criterion 13)
- 5. Osteoporotic compression fracture within 12 months prior to informed consent which is clinically significant in the opinion of the investigator.
- 6. Patient who must or wishes to continue the intake of restricted medications or any drug considered likely to interfere with the safe conduct of the trial.
- 7. Previous treatment in this trial.
- 8. Treatment with a systemic anti-cancer therapy or investigational drug within 28 days or 5 half-lives (whichever is shorter) of the first treatment with the study medication.
- 9. Any history of or concomitant condition that, in the opinion of the investigator, would compromise the patient's ability to comply with the study or interfere with the evaluation of the safety and efficacy of the test drug.
- 10. Women who are pregnant, nursing, or who plan to become pregnant or nurse during the trial or within 6 months after the last dose of study treatment.
- 11. Active alcohol or drug abuse in the opinion of the investigator.
- 12. Patient unwilling or unable to comply with the protocol.
- 13. Presence or history of uncontrolled or symptomatic brain or subdural metastases, unless considered stable by the investigator and local therapy was completed. Use of corticosteroids is allowed if the dose was stable for at least 4 weeks. Inclusion of patients with newly identified brain metastasis/es at Screening will be allowed if patients are asymptomatic.
- 14. Known history of human immunodeficiency virus (HIV) infection or an active hepatitis B or C infection which in the opinion of the investigator may interfere with participation in the trial.
- 15. History of Grade 3 hypersensitivity reactions (including cytokine release syndrome) to monoclonal antibodies.
- 16. History of allergy to kanamycin or similar class drugs (including streptomycin, gentamicin, amikacin, tobramycin and neomycin).

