4.1.6.2 Management of infusion-related reactions

Infusion-related reactions involve the immune system; however, they can have different mechanisms. Some are allergic in nature and are usually mediated by immunoglobulin E while others are not classical allergic reactions (so-called anaphylactoid reactions, e.g., caused by cytokine release). Although infusional reactions can be allergic or nonallergic, clinical symptoms are difficult to distinguish and require rapid assessment and immediate management to avoid severe AEs, including fatality.

If an infusion-related reaction of \geq CTCAE Grade 3 occurs, study treatment must be permanently discontinued.

If symptoms of an infusion-related reaction of CTCAE Grade 2 occur, which do not qualify as a DLT, the infusion should be temporarily stopped. Upon recovery, the following guidance must be followed:

- If more than 50% of the planned dose of BI 905681 was administered, no further BI 905681 will be administered until the next scheduled dose.
- If less than 50% of the planned dose of BI 905681 was administered due to IRR/CRS, a further dose of 50% of the intended total dose may be administered on the following day and after recovery to baseline for at least 24 hours.
- During the first re-exposure patients should be hospitalised for at least 24 hours and closely monitored.
- Premedication must be used for all subsequent treatment infusions. The recommended premedication is:
 - Acetaminophen/Paracetamol 650 mg - 1000 mg p.o., or equivalent
 - Antihistamine p.o. or i.v., equivalent to diphenhydramine 50 mg i.v.
 - Glucocorticoid i.v., equivalent to prednisolone 50-100 mg
- The infusion rate for further treatment cycles may be adapted according to Investigator decision, but any adaption of the infusion rate must be agreed with the sponsor.

If infusion reactions and/or hypersensitivity reactions occur in a substantial proportion of treated patients without premedication, the SMC may decide that all future patients treated in the study must receive premedication (as described above) prior to BI 905681 infusion; the

dosage and schedule of premedication will be aligned and will take into account any local clinical standards. Such a decision will be communicated to all investigators in writing.

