4.1.6.3 Management of Cytokine Release Syndrome (CRS)

Cytokine release syndrome is a disorder characterised by fever, tachypnea, headache, tachycardia, hypotension, rash, and/or hypoxia caused by the release of cytokines. As outlined above in [Section 4.1.6.2](#), clinical manifestations of CRS and other forms of infusion-related reactions are difficult to distinguish (especially at first occurrence) and require rapid diagnosis and immediate management to avoid severe AEs, including fatality.

Patients will be closely monitored for potential signs and symptoms of CRS (e.g., hypotension, rash, tachypnea, hypoxia, tachycardia, fever, nausea, fatigue, headache, myalgias and malaise). Patients must remain under observation for potential signs and symptoms of cytokine release for at least 6 hours following the end of infusion of BI 905681. If no signs or symptoms are observed during the first three administrations, the duration of observation may be reduced to 3 hours for subsequent administrations. For patients who require systemic steroids administered due to CRS around the time of administration of BI 905681 or during the post-treatment monitoring period, hospitalisation and monitoring for at least 24 hours is mandatory.

Body temperature, pulse rate and blood pressure will be measured prior to the start of infusion, every 30 minutes (± 10 minutes) during the infusion, and then at the following regular intervals during the post-treatment observation period:

- every 30 minutes (± 10 minutes) during the first 3 hours after end of infusion
- every hour (± 10 minutes) between 3-6 hours after end of infusion (if relevant)
- every 4-8 hours from 6 hours after end of infusion until observation ends (if relevant)

In case of suspected or confirmed CRS, patients will be appropriately treated according to best medical judgement based on institutional standards and/or publications (e.g.[R16-2323](#)). Supportive therapy including antipyretics, intravenous fluids, and low dose vasopressors may be used. In patients who do not respond to this, corticosteroids and/or interleukin 6 receptor antagonists ([R15-0031](#), [R18-1685](#), [R18-1686](#)) may be required and patients should be monitored closely, preferably in an intensive care unit.

In the event of CTCAE \geq Grade 3 CRS study treatment must be permanently discontinued.

In the event of CTCAE Grade 2 CRS the guidance for handling a CTCAE Grade 2 infusion-related reaction must be followed ([Section 4.1.6.2](#)).

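### Exclusion criterion 15 bars a past Grade 3 reaction to monoclonal antibodies but, read literally, not a past Grade 4 one

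*Protocol*

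**What the plan says.** Criterion 15 in Protocol Section 3.3.3 excludes patients with "History of Grade 3 hypersensitivity reactions (including cytokine release syndrome) to monoclonal antibodies". The synopsis carries the same wording, and Global Amendment 1 (Section 11.1) does not list the criterion among its changes.

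The protocol grades the same kinds of event in three other places:

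- **Section 3.1.1** has two separate triggers for a temporary stop to enrolment. For Grade 3 CRS, hypersensitivity or infusion reaction, the trigger is more than 20% of the patients at a dose level. For Grade 4 it is a single patient: "One patient experiences a Grade 4 CRS and/or Grade 4 hypersensitivity reaction and/or Grade 4 infusion reaction".
- **Section 4.1.6.2:** "If an infusion-related reaction of \geq CTCAE Grade 3 occurs, study treatment must be permanently discontinued".
- **Section 4.1.6.3:** "In the event of CTCAE \geq Grade 3 CRS study treatment must be permanently discontinued".

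Criterion 3, in the same list as criterion 15, is also written as a floor: "Osteoporosis \geq CTCAE Grade 2".

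The general criterion that might catch such a patient is number 9, which begins "Any history of or concomitant condition that, in the opinion of the investigator". It goes on to conditions that would compromise compliance or interfere with evaluating the drug. Criterion 16 concerns allergy to kanamycin-class drugs only.

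**The concern.** An eligibility rule that names one grade covers that grade only. Applied as written, criterion 15 turns away a patient with the less severe history and lets through one with the more severe history. No rationale for that ordering is given.

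The setting makes the gap worth closing. This is a first-in-human infused biologic, which Section 1.1 introduces as an antibody. The protocol takes infusion reactions and CRS seriously: patients in a cohort are treated at least 72 hours apart (Section 3.1), they are observed for at least 6 hours after early infusions (Section 4.1.6), and these reactions are AESIs whatever their grade (Section 5.2.6.1).

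Two things are at stake. The first is the safety of a patient admitted with that history. The second is conduct: one Grade 4 reaction in such a patient is enough for the enrolment stop in Section 3.1.1, which makes no exception for cause.

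**Working it through.** No arithmetic lies behind this criterion, so the check is a comparison of texts.

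| Place in the protocol | Event | Grade as written |
|---|---|---|
| 3.3.3, criterion 15 | Past hypersensitivity or CRS to monoclonal antibodies | 3 |
| Synopsis, same criterion | Same | 3 |
| 3.1.1, proportion rule | CRS, hypersensitivity, infusion reaction | 3 |
| 3.1.1, single-patient rule | Same three events | 4 |
| 4.1.6.2 | Infusion-related reaction | 3 and above |
| 4.1.6.3 | CRS | 3 and above |
| 3.3.3, criterion 3 | Osteoporosis | 2 and above |

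1. **Is a sign missing only from the extracted text?** Unlikely. The sign survives in criterion 3 of the same list, and both copies of criterion 15 lack it.

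2. **Can the bare grade mean that grade or worse?** Not on the protocol's usage for these events. Section 3.1.1 uses the bare grade for a category distinct from Grade 4 and gives each its own trigger. Where a floor is meant for infusion reactions and CRS, Sections 4.1.6.2 and 4.1.6.3 write one.

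3. **Does the protocol itself rank Grade 4 as graver?** Yes. With one event among n patients at a dose level, the Grade 3 rule needs 1/n > 0.20. That holds at n = 4 (25%) but not at n = 5 (20%). The Grade 4 rule is met by one event at any n. It is therefore never the weaker rule, and from five patients upwards it is stricter.

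4. **Does another criterion close the gap by rule?** No. Criterion 16 covers a different drug class. Criterion 9 names neither hypersensitivity, CRS nor a grade, and depends on opinion.

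5. **What would a source-document check show?** Section 8.3.1 requires documented evidence that no exclusion criterion is met. On the literal wording, a patient whose only such history is Grade 4 passes criterion 15.

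**The case against.** **The drafting is not uniform.** The DLT list in Section 4.1.7 names Grade 3 neutropenia with documented infection without a floor. Its separate Grade 4 neutropenia item needs more than 7 days. Read strictly, a shorter Grade 4 neutropenia with infection falls outside both lines, so a bare grade can stand where a floor is the sensible reading. This stands as evidence of a slip rather than an intention to admit such patients. It does not repair criterion 15, because for these particular events the protocol does separate Grade 3 from Grade 4.

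**A backstop exists.** A past Grade 4 reaction plainly invites use of criterion 9, and many investigators would apply it. Entry would need someone both to read criterion 15 literally and to decline to use criterion 9. That lowers the likelihood but leaves the outcome to each site's judgement.

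**The drug's own risk is not shown to be high.** Section 1.4 reports no CRS signal in the monkey study and no reported CRS with the other Wnt-pathway compounds cited. Staggered dosing, observation and discontinuation rules manage what risk remains. So the documents do not establish how likely a recurrence would be.

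**Stronger readings to avoid.** A reader might infer that one such reaction would end the trial. Section 3.1.1 provides a temporary stop with SMC review; discontinuation follows only if benefit-risk is no longer positive.

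A reader might also infer that the reaction would automatically enter the BLRM as a DLT and distort escalation. Section 4.1.7 makes DLT status subject to review, exempts events unequivocally due to an extraneous cause, and provides for a further judgement on whether a toxicity counts for escalation. The next dose is an SMC decision that also uses other data.

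Table 10.3:1 does show what one DLT can do. With none through 4.5 mg/kg, 6.5 is allowed with an overdose probability of 0.057 (scenario 7). With one at 4.5, the next dose stays at 4.5, with an overdose probability of 0.116 (scenario 3). But that shift follows any DLT in any patient, so it does not measure this defect.

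**Conclusion.** The point holds on the text. Criterion 15, in both places, fails to exclude by rule a history graver than the one it excludes, and it is out of step with Sections 3.1.1, 4.1.6.2 and 4.1.6.3. It is most likely a drafting slip.

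Its reach is eligibility and patient safety. It changes no planned analysis, prior, MTD definition or sample size. The number of patients affected is probably very small, but the documents give neither the frequency of such histories nor a recurrence risk, so no numerical size can be given. The one firm consequence is conditional: if such a patient had a Grade 4 reaction on study, enrolment would stop temporarily.

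The conclusion assumes that sites apply the criterion literally and that criterion 9 is not invoked. SAP Section 4 states that the trial is to be terminated early because of enrolment issues, so the practical value lies in any further protocol version or a successor protocol that carries the criterion over.

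**What to change.** Reconcile criterion 15 in Section 3.3.3 and its synopsis copy with Sections 3.1.1, 4.1.6.2 and 4.1.6.3. The sponsor should state explicitly which grades of past reaction are excluded, in the same words in both places, so that a more severe history is not admitted where a less severe one is barred. If a different treatment of Grade 4 was intended, the protocol should say so and give the reason. Which grades to exclude is the sponsor's clinical decision.

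The cost is a short wording change in two places, with no effect on sample size or analysis. If the clarified wording excludes more grades, at most a very few candidates would become ineligible. For this trial the change is worth making only if a further version is issued; otherwise it should be carried into any successor protocol that reuses the criterion.
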